The introduction of prostate-specific antigen (PSA) in screening strategy for prostate cancer has led to more tumors to be diagnosed at earlier stages with more indolent course that doesn't pose significant risk if left untreated (3). According to the European randomized study of screening of prostate cancer (ERSPC) trial, almost half of those who had surgery were found to have clinical indolent cancers (4). With the significant complication rates of radical therapies (erectile dysfunction seen in 24-90%, urinary incontinence in 2-72% and rectal toxicity in 2-15% (5-8) This raised concerns about overdiagnosis and subsequently overtreatment affecting patient's quality of life.

Active surveillance has been introduced as an alternative treatment to patients with low- risk prostate cancers. However, the inconsistency in active surveillance strategies across centers, lack of a reliable tool to monitor disease progression and ultimately the associated anxiety of patients regarding their disease raise the demand for a treatment option that is as effective as radical therapy while having a substantially low (if any) adverse effect, preserving patient's quality of life.

Focal therapy techniques have been introduced to fill the gap in prostate cancer treatment paradigm. It aims to destroy the tumor itself with adequate safety margin with the advantage of preserving the surrounding non-cancerous tissue. Thus maintaining disease control at acceptable levels, while minimizing complications (4).

The notion of focal therapy applied to treat a neoplastic process that is notoriously known for its multifocal organ involvement warrants a close understanding of the pathological landscape of prostate cancer. Several studies have highlighted the concept of “index tumor” in prostate cancer where many patients with

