“*pathologically multifocal*” disease can be considered to have a “*biologically unifocal*” disease. Those patients are found to have a dominant focal tumor along with a smaller burden of non-dominant tumors that rarely contain higher grade disease than the main tumor and are therefore not considered the denominators for disease progression and are unlikely to affect the treatment outcome. Eliminating that dominant tumor focus with targeted therapy that spares the rest of the gland is therefore hypothesized to markedly reduce tumor burden and eradicate the likely source of extra-capsular tumor extension while potentially reducing morbidity and preserving the sexual, urinary, and bowel function (9-13).

With the advent of multiparametric MRI (Mp-MRI), it is now possible to identify suspicious prostate gland focal lesions, determining their extent and targeting them for biopsy and focal ablation.

Laser interstitial thermal therapy (LITT) is well suited for MRI environment. Laser fibers are flexible so they can fit into the MRI gantry, with no distortion of the electromagnetic field. (14) It has been shown to produce homogenous tissue necrosis that can be monitored by real time temperature maps, a feature that facilitates effective and safe ablation.(15-17)

Previous preliminary studies and phase I trials with short term follow ups, small patient populations showed the potential efficacy and safety of this technique.(18-23) Oto et al (19) trial using transperineal MRI guidance on 9 patients showed no significant change in quality of life parameters during follow up with short term treatment efficacy about 78 %. A more recent Phase I trial by Natarajan et al (23) using transrectal MRI guidance on 8 patients with intermediate risk disease showed absence of major complications and no changes of quality of life parameters and short term treatment efficacy about 62%. A recent phase II trial by Eggener et al (24) showed similar results on intermediate term follow up (at 1 year) regarding the quality of life parameters, however with recurrent tumors in 37 % of patients either in the ablation zone or outside the ablation zone.

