 - The transrectal piece will then be connected to the rest of the system. Preliminary imaging will be obtained to identify the transrectal fiducial line, the target lesion, and to calculate the trajectory angles in 3 planes.
 - Subsequently, a 14-gauge MR compatible co-axial puncture needle will be introduced into the target lesion via the transrectal approach along the calculated trajectory.
 - When the needle position is deemed satisfactory, a 1.5-cm-active tip diode laser fiber will be introduced within an internally cooled catheter through the introducing sheath.
 - The catheter tip location will be confirmed on TSE T2-weighted images in the axial and sagittal oblique planes.
 - The introducer sheath will be withdrawn to allow contact of the active laser tip with the lesion.

- A laser test dose will be done at 9 Watts for about 30 seconds to confirm the site of fiber placement with the subsequent delivery of full dose ablation at 12-27 Watts.
- Ablation duration is determined based on real time feedback of response using real time temperature and damage estimate maps.

Post procedure:

✓ *At the end of ablation:*

- Post procedure scans will be performed, consisting of axial, sagittal, coronal VIBE scans, before and after IV administration of gadolinium-based MR contrast agent.
- Additionally, axial, sagittal, and coronal high-resolution TSE T2-weighted images will be performed.

✓ *Starting at recovery:*

- Ibuprofen 400 mg oral tablet by mouth, every 6 hours.
- Tamsulosin 0.4 mg oral capsule by mouth, q24 hours.

✓ *After leaving the hospital:*

- Foley's catheter will remain for 3 days- will be removed in the radiology department. Subjects will be evaluated for urine obstruction or leak at that time.

• **Follow ups:**

- Immediately after the procedure, at 3 weeks, 3 months, 6 months, one year (primary end point) and two years (2ry end point) after procedure.
- All follow up visits will include mp-MRI, serum PSA, QOL questionnaires.
- In bore MRI guided biopsy will be done after one and two years for the ablation site and any other suspicious areas discovered in follow up scans. Biopsies outside these time points will be obtained if new MRI suspicious sites are noted on follow up MRIs or if PSA level is trending up.

• **Possible complications:**

- Urinary tract infection, sepsis

- Hematuria
- Urinary retention
- Erectile dysfunction
- Urinary incontinence
- Fecal incontinence
- Bleeding per rectum
- Recto-ureteral fistula

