- Urinary tract obstruction.

- **Outcome:**

Primary endpoint:

- Treatment Efficacy: measured by recurrence rate at 1-year post-ablation (i.e. number of recurrences/number of subjects).

Secondary endpoint:

- Recurrence rate at two-year post ablation time point.

**recurrences are defined as any newly developed mpMRI abnormality contiguous with the ablation zone and proved by subsequent targeted biopsy.

- Methods of assessment (each follow up visit):
 - Mp-MRI scans with each follow up visit:
 - Ablation zone: assessed for residual tumor.
 - Non-ablated areas: for new tumor(s).
 - MRI guided biopsy for the ablation site after one and two years or if a suspicious lesion developed during follow-ups.
 - Serum PSA.
- Safety and functional outcomes:

- Complications: Grade 3 complications or higher as defined as National cancer institute's common toxicity criteria version 4: *incontinence or urinary retention necessitating surgical intervention or new-onset erectile dysfunction not responsive to medication.*
- *Urinary function* → will be assessed by IPSS at baseline pre-ablation visit and with each follow up visit.
- *Erectile function* → will be assessed by SHIM baseline pre-ablation visit and with each follow up visit.
- Other Procedural complications: Infection, bleeding, hematuria, fistula.

Participant timeline:

**Each follow up time point is calculated from the previous visit, not from procedure date

Recruitment strategy:

- We will rely on either physician referral or self-referral.
- Self-referred subjects will be counseled about standard of care treatment options. For these subjects, the study team will document evaluation by a radiation oncologist for each participant and decline of the recommended modality.
- No financial incentives will be offered.

- Posting basic descriptive information on ClinicalTrials.gov

Informed consent:

- Informed consents will be obtained in person on 1st visit in a private room.
- Subjects will be allowed time to discuss with others before deciding to enroll.
- The study process and details will be discussed verbally with the patients.
- Time will be allowed for questions.
- A hand-out will be provided to the patients with frequently asked questions.

Data collection & management:

- All patients' data will be documented in the electronic medical records (powerchart) through the standard clinical process.
- All treatment-related hard copy documents will be scanned into the electronic medical records (powerchart).

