The primary endpoint is the recurrence rate at 1 year, defined as the number of recurrences divided by the number of patients. For this study, Simon's two-stage design will be utilized, using the Minimax design. (25, 26) The null hypothesis that the true recurrence rate is 0.49 will be tested against a one-sided alternative. In the first stage, 18 patients will be accrued. If there are 6 or more recurrences in these 18 patients, the study will be stopped. Otherwise, 2 additional patients will be accrued for a total of 20. The null hypothesis will be rejected if 6 or fewer recurrences are observed in 20 patients. This design yields a type I error rate of 0.05 and power of 0.8 when the true recurrence rate = 0.22.

Recurrence rate at 1 year, as well as at follow-up visits at 3 weeks, 3 months, 6 months, and 2 years will be estimated, and exact 95% confidence intervals will be estimated using the Clopper-Pearson method (27). Number of complications and rate of complications will be summarized using frequencies and percentages. Additionally, all numeric patient characteristics will be summarized using mean, standard deviation, median,

and range, and all remaining categorical patient characteristics will be summarized using frequencies and percentages. No loss to follow-up is expected.

Erectile function and urinary function will be summarized at baseline and at each follow-up visit using Quality of Life (QoL) assessments – SHIM for erectile function and IPSS for urinary function. Scores will be aggregated across questions, and grouped into ordinal categories. For each QoL measurement, frequencies and proportions of each ordinal category will be reported at baseline and at each follow-up visit. To assess the measurements longitudinally, we will consider an ordinal logistic regression model using a generalized estimating equations (GEE) approach for handling correlation within patients in order to evaluate the impact of time on erectile and urinary function.

Stopping rules for safety are detailed in the DSMP section below.

Data and safety monitoring plan (DSMP):

The PI will ensure that the protocol is conducted in a consistent manner and that all PHI from the study obtained is handled in a HIPAA compliant manner.

1. Monitoring the Progress and Safety of the Trial

a. What are the potential risks and benefits for study participants?

Risks:

- Urinary tract infection, sepsis
- Hematuria
- Urinary retention
- Erectile dysfunction
- Urinary incontinence

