- Fecal incontinence
- Bleeding per rectum
- Recto-ureteral fistula
- Urinary tract obstruction.
-

The benefit to the patient is receiving a standard treatment protocol with the possibility of extra imaging which may enhance the diagnostic ability of the physician. Subject participation may help future patients having this same procedure.

b. What is the screening process and how it will be used to protect participants?

MRI scans will be conducted only on patients who require a clinically indicated MRI as determined by a urologist and/or a radiologist, who have no additional contraindications to MRI, and who do not meet other exclusion criteria for MRI. When the patient arrives for MRI (or if seen earlier at the interventional MRI clinic as a part of pre-procedure evaluation), he will undergo routine screening to ensure the absence of any incompatible implants or devices, screening and consent for intravenous contrast (if clinically indicated) making sure there are no contraindications to contrast if contrast is indicated.

c. What are the measures to protect participants against risk?

Patients will be initially counseled about the current standard of care treatments available and that the study procedure is experimental. The study team will document evaluation by a radiation oncologist for each self-referred participant and decline of the recommended modality.

Proper identification of cancerous lesion(s) will be performed with pre-treatment multiparametric MRI to assess the technical appropriateness of MRI guided focal laser ablation. Prior to starting the ablation procedure, normal saline may be infused into the recto-prostatic space (hydro-dissection) to protect the rectum from injury during ablation if that process is deemed necessary on pre-procedure imaging. Subjects undergoing the treatment procedures will benefit from real-time monitoring with temperature maps and damage estimate maps performed online as the ablation procedure is being conducted. Additionally, an immediate post-procedure new baseline MRI of the prostate will be performed before the subjects leaves the MRI unit. This will also be used to evaluate for and manage any immediate complications.

Procedures will be performed on an out-patient same-day surgery basis. Subjects will recover in the standard recovery area and discharged on the same day unless a complication occurs.

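### Fecal incontinence is a named risk and bowel preservation is part of the rationale, but no bowel-function measure is specified at baseline or follow-up, so cases below surgical severity depend on spontaneous report

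*Combined protocol and SAP*

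**What the plan says.** The background names three domains of harm after radical therapy: erectile, urinary and rectal, the last as "rectal toxicity in 2-15" per cent. It then presents focal ablation as "potentially reducing morbidity and preserving the sexual, urinary, and bowel function". The first stated goal of the trial is to evaluate functional outcomes, glossed as safety.

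"Fecal incontinence" appears in the list of possible complications and again among the risks in DSMP section 1a, together with rectal bleeding and a fistula. One of the two approaches is transrectal, and DSMP section 1c says that "normal saline may be infused into the recto-prostatic space (hydro-dissection) to protect the rectum from injury".

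Under Safety and functional outcomes, the Grade 3 or higher definition includes "incontinence or urinary retention necessitating surgical intervention", followed by "Other Procedural complications: Infection, bleeding, hematuria, fistula". Urinary and erectile function are the only functions assessed at each visit. Quality-of-life questionnaires are required at baseline and at every follow-up visit, and the Statistical analysis plan identifies them as "SHIM for erectile function and IPSS for urinary function". The follow-up list in Data collection & management has imaging, biopsy, PSA, SHIM, IPSS and urinary continence. It has no bowel item.

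**The concern.** Of the three functional domains that the protocol sets up, two have an instrument, a baseline, repeated measurement and a longitudinal model. The third has none of these, although the procedure carries a recognised risk to the rectum.

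Two things are at stake. First, new leakage or urgency that does not need surgery may go unrecorded unless the patient mentions it, so a low count would be hard to interpret. Second, bowel status before ablation cannot be measured afterwards. Without it, a symptom reported later is difficult to separate from one already present.

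**Working it through.** The plan gives no figure for bowel outcomes, so the main check sets the capture routes side by side.

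| Bowel harm | Where it could be recorded | Baseline value | Asked at each visit |
|---|---|---|---|
| Rectal bleeding | Other procedural complications (bleeding) | No | No |
| Fistula | Other procedural complications (fistula) | No | No |
| Fecal incontinence needing surgery | Grade 3+ definition, if incontinence includes fecal | No | No |
| Fecal incontinence or urgency not needing surgery | No explicit outcome; spontaneous report only | No | No |

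The other routes do not close the last row:

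- Data collection & management has a complication field only for immediate complications, under procedure data. The follow-up list has none.
- The check at catheter removal concerns urinary obstruction or leak.
- The unanticipated-problem grades in DSMP section 2a concern effects of new pulse sequences (grades 1 and 2) and death (grade 3). The stopping rule in section 1e counts those events, so fecal incontinence falls outside it.
- The DSMC reviews adverse events and aggregate toxicity, but it can review only what was recorded.

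**Illustrative scale.** Inputs: n = 20 (Recruitment Goal) and an assumed rate of 2% to 15%, borrowed from the radical-therapy range in the background.

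- Expected cases: 20 × 0.02 = 0.4 and 20 × 0.15 = 3.0.
- Chance of at least one case, 1 − (1 − p)^20: 1 − 0.98^20 = 0.332 and 1 − 0.85^20 = 0.961.

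This range is for rectal toxicity as a whole after a different treatment. It is not a rate of fecal incontinence after laser ablation, and it may include events such as bleeding that the plan does list.

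**What full collection could show.** With zero events, the Clopper-Pearson two-sided 95% upper limit is 1 − 0.025^(1/n).

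- n = 20: 1 − 0.025^(1/20) = 0.168.
- n = 18, if the trial stops after stage 1: 1 − 0.025^(1/18) = 0.185.

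Both limits lie above 15%, the top of the cited range.

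**Effect on the design.** The two-stage rule is: stop at 6 or more recurrences in 18; reject if 6 or fewer in 20. Summing P(X1 = x; 18) × P(X2 ≤ 6 − x; 2) over x = 0 to 5 gives 0.048 at a recurrence rate of 0.49 and 0.805 at 0.22. These agree with the stated 0.05 and 0.8. Adding bowel items leaves this calculation and the sample size unchanged.

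**The case against.** A reader might infer that the trial cannot detect fecal incontinence at all, or that any bowel harm would leave no trace. The documents do not support that. Bleeding and fistula are listed outcomes, and since hematuria is listed separately, bleeding most naturally includes rectal bleeding. The Grade 3 or higher wording is ambiguous rather than silent. Fecal incontinence is a named possible complication, and the Statistical analysis plan summarises complications without restricting their type. Spontaneous reports can enter the medical record and reach the DSMC. The data list is introduced in non-exclusive terms and includes past medical history. This part of the objection stands, and it confines the point to non-surgical fecal incontinence or urgency and to change from baseline. These routes are passive, however, and do not replace asking.

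It can also be said that no bowel claim is planned, because preservation is only hypothesised in the background. That is fair, but the risk is named for this procedure and functional safety is the first goal, so the gap does not depend on a planned claim.

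The in-house series of 14 cases without complications gives limited reassurance: 0 of 14 has an upper limit of 1 − 0.025^(1/14) = 0.232, and the text does not say how bowel symptoms were sought.

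Finally, a bowel measure in 20 men would not prove safety. That is correct. A split by approach would be weaker still: assuming 10 men per group, 0 of 10 gives 1 − 0.025^(1/10) = 0.308. Such a split should not be a required analysis. Erectile and urinary function will also be studied in only 20 men, and the plan still measures them.

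The participant timeline shows only a footnote in the text available for review, so the point rests on the readable sections.

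**Conclusion.** The point holds as a modest, inexpensive improvement to safety data collection. Followed as written, the plan would not systematically collect fecal incontinence or urgency below surgical severity and could not assess change from baseline in bowel function. Rectal bleeding and fistula are covered as complications, and surgical-severity fecal incontinence may be.

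The number of cases affected cannot be derived from the documents. The 0.4 to 3 expected cases, and the 33% to 96% chance of at least one, rest on applying radical-therapy rectal toxicity to this procedure. They show scale only and do not count cases the plan would miss. With complete collection, zero events in 20 would still be compatible with a true rate of up to 16.8%, so the gain is an interpretable description. The primary endpoint and its design are unaffected.

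**What to change.** 1. In Pre-intervention investigations, Follow ups and Data collection & management, add a few items on fecal incontinence and urgency (by CTCAE grade or as short patient-reported items) to the questionnaires already given at baseline and each follow-up visit.
2. Under Safety and functional outcomes, list fecal incontinence as an outcome and state whether incontinence in the Grade 3 or higher definition includes fecal.
3. In the Statistical analysis plan, report new or worsened cases against baseline as counts and percentages with Clopper-Pearson 95% intervals, the method already chosen for recurrence. Label the result as descriptive.

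The cost is an amendment to these sections and a small added patient burden at visits that already include questionnaires. No extra procedure, visit or patient is needed. The baseline items should be in place before the first ablation, because they cannot be recovered afterwards.

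### The only recurrence-based stop comes at 18 of 20 patients; an added stop at 12 would cost no type I error or power and lower expected enrolment under the null from 18.1 to 15.3

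*Combined protocol and SAP*

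**What the plan says.** The Statistical analysis plan section sets the endpoint: "The primary endpoint is the recurrence rate at 1 year, defined as the number of recurrences divided by the number of patients". It then states that "Simon's two-stage design will be utilized, using the Minimax design", and gives the hypothesis: "The null hypothesis that the true recurrence rate is 0.49 will be tested against a one-sided alternative".

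The rule has two stages. Stage 1 runs to 18 men, where a futility rule applies: "If there are 6 or more recurrences in these 18 patients, the study will be stopped". A trial that passes this look goes on to its full size of 20, and success is then judged on the whole sample: "The null hypothesis will be rejected if 6 or fewer recurrences are observed in 20 patients".

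The claimed operating characteristics are: "This design yields a type I error rate of 0.05 and power of 0.8 when the true recurrence rate = 0.22".

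No other stop depends on recurrence. The stopping rule in the Data and safety monitoring plan counts unanticipated problems, which that section grades as effects of new pulse sequences or death. The sentence on the second stage ("Otherwise, 2 additional patients will be accrued for a total of 20") makes the last two men conditional on the first 18, and so implies that accrual waits for the 18-patient result, but the plan does not state a hold.

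**The concern.** A two-stage design is normally chosen to limit the number of patients given a treatment that does not work. Here the single look comes at 90% of the sample (18/20). The monitoring plan itself tells patients that the procedure is experimental, and its risk list includes sepsis, fistula and incontinence. If the true recurrence rate were 0.49, the rule would very probably detect it, but only after 18 of the 20 men had been treated. The endpoint takes a year to read, so the implied wait at 18 buys protection for two patients only. The question is whether an earlier stop can be had without losing the stated type I error and power and without enrolling more than 20.

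**Working it through.** **Inputs**, all from the Statistical analysis plan: p0 = 0.49, p1 = 0.22; stage 1 n = 18, stop at 6 or more; total 20, success at 6 or fewer. Write b(x; n, p) for the binomial probability and Xn for the number of recurrences in the first n men.

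**1. The plan's own figures.** Success needs X18 ≤ 5 and X20 ≤ 6. With X18 ≤ 4 the last two men cannot change the result. With X18 = 5 success fails only if both recur. So

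P(success) = P(X18 ≤ 5) − b(5; 18, p) × p²

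- p = 0.49: 0.0572 − 0.0382 × 0.2401 = 0.0572 − 0.0092 = **0.0481**
- p = 0.22: 0.8134 − 0.1747 × 0.0484 = 0.8134 − 0.0085 = **0.8049**

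Both agree with the stated 0.05 and 0.8. A search over all two-stage futility designs found this to be the only one with N = 20 that meets both limits, and none with fewer patients.

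**2. What the look at 18 saves.** The probability of stopping at 18 is 1 − 0.0572 = 0.943 at 0.49 and 1 − 0.8134 = 0.187 at 0.22. Expected N at 0.49 is 18 + 2 × (1 − 0.943) = **18.1**.

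**3. Add: stop if 6 or more of the first 12 recur.** If X12 ≥ 6 then X18 ≥ 6, so every trial stopped here would have been stopped at 18 anyway. P(success) is therefore unchanged at 0.0481 and 0.8049.

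- Stopping probability: P(X12 ≥ 6) = 0.585 at 0.49 and 0.030 at 0.22.
- Expected N at 0.49, if accrual then runs to 20: 12 + 8 × (1 − 0.585) = **15.3**.

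**4. Alternative: stop if 5 or more of the first 10 recur.** The only lost successes are those with 5 recurrences in the first 10, none in the next 8, and not both of the last two:

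Loss = b(5; 10, p) × (1 − p)⁸ × (1 − p²)

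- p = 0.49: 0.2456 × 0.00458 × 0.7599 = 0.0009, so type I error is 0.0481 − 0.0009 = **0.0472**
- p = 0.22: 0.0375 × 0.1370 × 0.9516 = 0.0049, so power is 0.8049 − 0.0049 = **0.8000** (0.80003 unrounded)
- Stopping probability: 0.598 at 0.49 and 0.048 at 0.22.
- Expected N at 0.49: 10 + 10 × (1 − 0.598) = **14.0**.

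**5. What does not work: moving the look and dropping the 18-patient criterion.** With a look at 10 and success at 6 or fewer of 20:

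| Continue if | Type I error | Power |
|---|---|---|
| 3 or fewer of 10 | 0.0522 | 0.789 |
| 4 or fewer of 10 | 0.0654 | 0.857 |

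Neither meets both limits.

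**6. The price of the early look.** If accrual runs to 20 after the look at 12, trials in which 6 or more of the first 18 eventually recur are no longer cut off at 18. Their probability is 0.943 − 0.585 = 0.357 at 0.49 (unrounded inputs) and 0.187 − 0.030 = 0.156 at 0.22. For the look at 10 the figures are 0.346 and 0.144.

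**The case against.** The strongest reply is that nothing is wrong. The plan names the minimax criterion, which minimises the maximum sample size, and delivers exactly that design with correct error rates. Preferring a smaller expected sample is a choice between valid designs. That stands.

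Two stronger readings are tempting, and the documents support neither.
- A reader might infer that the second stage is idle, because it changes the verdict with probability of only about 0.009 at 0.49. But a rule of 5 or fewer of 18 alone has type I error 0.0572. The last two men bring it down to 0.0481, so stage 2 is what makes the test meet 0.05.
- A reader might infer that the look can simply be moved to patient 10. Step 5 shows that it cannot. The earlier stop works only if the 18-patient cut-off is kept as a success criterion, and the result is then no longer a plain Simon two-stage rule.

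The early look also has costs. A trial that passes it treats all 20 men, whatever the first 18 later show. The verdict at 6 recurrences of 20 depends on treatment order: with the look at 10, the chance at 0.22 of completing 20 men with 6 recurrences and failing because all six fell in the first 18 is 0.057. Under the plan that trial would have stopped at 18, so the verdict is the same but two more men are treated. No time is saved when the trial continues, since there is still one hold and a final year of follow-up. The look at 10 leaves almost no margin above 0.8 power. These points favour the look at 12 over the look at 10, but they do not remove the gain under the null.

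**Conclusion.** The concern holds as a design improvement. The plan's design is valid and its figures are right, but its only recurrence-based stop protects at most 2 of 20 men. An added stop at 6 or more of the first 12 leaves type I error and power exactly as they are and lowers expected N at 0.49 from 18.1 to 15.3, about 2.8 men fewer. The look at 10 lowers it to 14.0, about 4.1 men fewer, at a cost of 0.005 in power.

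These savings assume that accrual is held at the early look until the 1-year results are in. The plan implies such a hold at 18 but does not state it, and the documents give no accrual rate. Without a hold, later patients may already have been treated when the look is read, and the saving shrinks; the same is true of the plan's own look at 18. The calculations also use the plan's assumption of no loss to follow-up.

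**What to change.** Amend the Statistical analysis plan as follows.
1. Add a futility stop: the study stops if 6 or more of the first 12 men have a recurrence at 1 year.
2. State that accrual is held after patient 12 until those 1-year results are known, in place of the hold implied at 18, and then runs to 20.
3. Keep both success criteria: 5 or fewer recurrences among the first 18 in order of treatment, and 6 or fewer among all 20.
4. Report the exact operating characteristics: 0.0481 and 0.8049, stopping probability 0.585 at 0.49 and 0.030 at 0.22, expected N 15.3 at 0.49.

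If more protection is wanted, use 5 or more of the first 10 instead and report 0.0472, 0.800 and expected N 14.0, accepting a 4.8% chance of stopping at 10 when the true rate is 0.22.

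The cost is a change to the protocol and SAP text. The design should then be described as a minimax rule with an added early futility look. Maximum N and the number of holds do not change. What is given up is the operative stop at 18. If the sponsor prefers the present rule, it should say why the look is so late and state whether accrual is held at 18.
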